## **2.2 Prior clinical experience**

The principal investigator for this study has been using TXA in his clinic as an off-label drug for the treatment of small bowel AEs. Those who were treated with TXA were those patients that have failed standard therapy. Failure of standard therapy is defined as continued GI bleeding and need for blood transfusions despite endoscopic ablation, octreotide therapy and iron supplementation for at least 3-6 months. Thus far, 9 patients have been treated with TXA therapy consisting of 650 mg oral tablets taken three times per day for 3 months. In 8 of those patients there was an observed clinical response defined as stabilization of hemoglobin which was not previously achieved with prior therapy. Although this sample size of patients was not a controlled study accounting for confounding variables, it does strongly highlight the potential beneficial therapeutic effects of TXA. Of note, there were no side effects observed by the 9 patients.

## 3 - Rationale/Significance

### 3.1 Problem Statement

The current management of small bowel AE's is suboptimal as the majority of patients with symptomatic bleeding experience continued or recurrent bleeding despite standard of care therapy including endoscopic ablation, octreotide and iron supplementation. In these cases, patients may require repeated transfusion of PRBC's as palliative treatment which is a source of morbidity including repeated hospitalization and is often complicated over time by transfusion reactions, iron overload, and volume overload. Patients with severe disease may develop antibodies to all blood products over time such that they can no longer tolerate PRBC transfusion.

### 3.2 Purpose of Study/Potential Impact

Currently, the mainstay of treatment for intestinal AEs includes endoscopic ablation combined with octreotide and iron supplementation. However, many patients continue to suffer from persistent or recurrent symptomatic anemia and often require repeated hospitalizations for blood transfusions. TXA is a hemostatic agent that has the potential to be beneficial in patients with small bowel GI bleeding. Through our literature review multiple case reports have highlighted the impact TXA treatment can have on patients with intestinal AEs. Our study would help determine the potential additive effect of TXA in patients with symptomatic anemia due to GI AE's. Further, we seek to expand our knowledge of the applications of TXA with the goal of decreasing morbidity and mortality.

### 3.3 Potential Risks and Benefits

#### 3.3.1 Potential Risks

Adverse events will include medication side effects including nausea, vomiting, diarrhea, rash, itching, hypotension, and thromboembolic events. These side effects will be closely monitored through monthly in person or virtual interviews with patients for the entirety of the study period.

Thromboembolic events have the largest potential impact to patient's health and include deep vein thrombosis (DVT), pulmonary embolism (PE) and stroke. Dionne et al. recently published the largest systemic review and meta-analysis examining TXA in GIB and found that the absolute risk of thromboembolic events to be <2%. This presents a small but statistically significant risk of DVT/PTE with high dose IV TXA but cannot be extrapolated to lower dose oral TXA regimens. Further, the safety profile of oral TXA has been confirmed and well-studied in the fields of trauma and orthopedics. Specifically, a large meta-analysis looking at the 5 RCTs comprising approximately 600 patients found no statistically significance increasing in thromboembolic complications between patients undergoing a total knee replacement who received oral TXA for intra/post-operative bleeding vs control patients. We do appreciate that certain populations of patients are at increased risk for thromboembolic events. These include comorbidities such as liver disease and malignancy. On literature review, specific rates of thromboembolic events in these populations with the use of TXA has not yet been studied. Importantly, a group of patients who may not know they would be at an increased risk are those with undiagnosed prothrombotic states. While it would not be possible to screen for all prothrombotic diseases, factor 5 Leiden and prothrombin mutation make up a large portion of hypercoagulable disorders. In order to screen out these patients, lab markers testing for the aforementioned disorders will be ordered in all patients during initial laboratory lab work.

### **3.3.2 Potential Benefits**

If TXA is shown to decrease the need for further blood transfusions and hospital admissions, it becomes a viable option for patients affected by intestinal AEs. Specifically, for patients who experience recurrent blood loss despite current standard medical therapy.

## 4 - Study Objectives

### 4.1 Hypothesis

We expect 75% of patients on TXA to have a 2 gm/dl improvement in overall hemoglobin while only 25% in placebo group see a 2gm/dl improvement. We expect 75% of TXA patients to require zero blood transfusions compared to placebo group requiring 1 blood transfusion on average per patient over 3 months.

### 4.2 Primary Objective

To determine whether oral therapy with TXA results in improvement in serum hemoglobin concentration and/or requirement for PRBC transfusion compared to placebo in patients treated with standard endoscopic ablation and iron supplementation

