**Primary Outcome Variables**

Primary outcome variables include hemoglobin concentration and the requirement of packed RBC transfusion.

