#### 5.2.2 Secondary and Exploratory Outcome Variables (if applicable)

Secondary outcome variables include number of hospitalizations, endoscopic interventions (EGD, Colonoscopy, enteroscopy, video capsule endoscopy) and experienced side effects.

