**Exclusion Criteria**

- Contraindications to TXA therapy
  - Allergy to TXA, intracranial bleed, history of venous or arterial thromboembolism, active thromboembolic disease, ischemic retinopathy
- Bleeding/Coagulopathy disorder and/or on anticoagulation regimen
- Ulcerative colitis or Crohn's disease
- End stage renal disease
- Decompensated cirrhosis
- Pregnancy or intention to become pregnant
- Patient refusal of blood products because the secondary outcome is pre-determined
- Unable to give formal consent
- Participation in another interventional study where primary outcome includes hemoglobin/hematocrit values
- Inability to adhere to treatment regimen for 3 months
- Non-English speaking
- Patients < 18 years old

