## **6.4 Statistical Method**

### **6.4.1 Sample Size Considerations**

We based our sample size estimate on assumptions for our primary aim, as this is the most important aim for providing information to support future recommendations with regards to TXA in patients with intestinal AE. A total of 50 subjects will be enrolled with 1:1 randomization to either TXA or placebo. For the primary study endpoint of hemoglobin, we will have 80% power to detect an average increase of 25% from baseline to 3 months between TXA and placebo groups ( $\alpha = 0.05$ ). We expect 75% of patients on TXA to have a 2 gm/dl improvement in overall hemoglobin while only 25% in placebo group see a 2gm/dl improvement. We expect 75% of TXA patients to require zero blood transfusions compared to placebo group requiring 1 blood transfusion on average per patient over 3 months.

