### **6.4.2 Planned Analyses**

We will characterize subjects with regard to baseline and follow up hemoglobin/hematocrit (H/H) and other endpoints previously described. We will summarize demographics and other predictors of clinical status. Continuous variables will be summarized by mean, standard deviation and range as appropriate. The primary analysis will compare the absolute and percent change in hemoglobin with adjustment for baseline in linear regression models. Using multivariable logistic regression models adjusting for baseline hemoglobin, we will assess if the odds of achieving a clinically relevant improvement in hemoglobin differs by treatment assignment. The secondary outcomes will be analyzed similarly using linear regression models adjusting for baseline values.

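### The plan does not settle whether transfusion is a primary outcome and states no success rule; if either outcome can carry the claim, the stated 5% error is exceeded

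*Combined protocol and SAP*

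**What the plan says.** Two groups of statements point in different directions.

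**Transfusion as primary.** The primary objective, in the synopsis and in 4.2, is "improvement in serum hemoglobin concentration and/or requirement for PRBC transfusion compared to placebo". The synopsis and 5.2.1 then state: "Primary outcome variables include hemoglobin concentration and the requirement of packed RBC transfusion".

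**Hemoglobin as the only primary.** Section 6.4.1 says: "For the primary study endpoint of hemoglobin, we will have 80% power to detect an average increase of 25% from baseline to 3 months". The alpha of 0.05 belongs to that sentence, and no other outcome is given an alpha or a power. Section 6.4.2 says: "The primary analysis will compare the absolute and percent change in hemoglobin with adjustment for baseline in linear regression models". The exclusion criteria in 5.3.2 include: "Patient refusal of blood products because the secondary outcome is pre-determined". In a criterion about blood products, that outcome is most naturally transfusion.

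**Transfusion is not placed among the secondaries either.** Section 5.2.2 reads: "Secondary outcome variables include number of hospitalizations, endoscopic interventions (EGD, Colonoscopy, enteroscopy, video capsule endoscopy) and experienced side effects". The synopsis list and the secondary objectives in 4.3 also omit it. It is therefore unclear whether the sentence in 6.4.2, "The secondary outcomes will be analyzed similarly using linear regression models adjusting for baseline values", reaches transfusion. The opening of 6.4.2 does promise to characterize subjects on the endpoints described before it, which gives transfusion a descriptive summary at most.

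**The transfusion hypothesis.** Sections 4.1 and 6.4.1 expect "75% of TXA patients to require zero blood transfusions compared to placebo group requiring 1 blood transfusion on average per patient". The TXA arm is described by a proportion and the placebo arm by a mean count.

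No section states a success rule, an alpha split, a testing order or a multiplicity adjustment.

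**The concern.** A result with a significant transfusion difference and a null hemoglobin difference would satisfy the objective in 4.2 and would not be a positive primary analysis under 6.4. Both reports could cite the protocol. As written, the choice between them, the form of the transfusion variable (any versus number) and its test could all be made after the data are seen.

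This outcome matters to the claim. Section 3.3.2 rests the potential benefit on fewer transfusions and hospital admissions, and 6.4.1 says the primary aim is meant to support future recommendations. What is at stake is whether the 5% in 6.4.1 describes the chance of a false positive claim. It does so only if hemoglobin, on one scale, is the sole route to that claim.

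**Working it through.** **Inputs from the documents.** 50 subjects, 1:1, so 25 per arm; alpha 0.05; 80% power for hemoglobin (all 6.4.1). 75% of TXA patients with no transfusion, so 25% transfused; placebo mean of 1 transfusion (4.1, 6.4.1).

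**Inputs assumed.** Two-sided testing, the correlation between the outcomes, the transfusion test and the null transfusion rate. The documents give none of these, so ranges are shown.

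**1. The plan's own figure.** The 80% power cannot be reproduced because no SD is given. With 25 per arm and a two-sided 5% t-test, 80% power needs a standardized difference of 0.809. If the 25% is a difference between arms in percent change, the implied SD is 25 / 0.809 = 30.9 points. Nothing below depends on this figure.

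**2. Hemoglobin alone decides.** One test at 0.05 gives 5%. Transfusion adds nothing.

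**3. Either outcome suffices, each test of size exactly 5% two-sided.** If independent, 1 − 0.95² = 0.0975. With correlation, the error is 1 − P(|Z1| < 1.96 and |Z2| < 1.96) under a bivariate normal:

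| Correlation | Error |
|---|---|
| 0 | 9.75% |
| 0.5 | 9.07% |
| 0.8 | 7.81% |
| 0.9 | 7.04% |

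The error tends to 5% as the correlation tends to 1. Counting only false claims in favour of TXA, the figures are 4.9% (correlation 0) down to 3.5% (0.9), against 2.5% for a single test.

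**4. Transfusion (any versus none) by Fisher's exact test, 25 per arm.** Fisher's true size is below 5%. With an independent 5% hemoglobin test, the error is 1 − 0.95 × (1 − size):

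| Null transfusion rate | Fisher size | Either suffices |
|---|---|---|
| 10% | 0.88% | 5.8% |
| 25% or 75% | 2.18% | 7.1% |
| 40% | 2.95% | 7.8% |
| 50% | 3.28% | 8.1% |
| 63% | 2.75% | 7.6% |

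Simulation with patient-level correlation 0.5 to 0.9 and null rates of 25 to 75% gives about 6.2 to 7.7%.

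**5. Transfusion (any versus none) by linear regression.** This is the only model type that 6.4.2 names for outcomes other than hemoglobin. With 25 per arm its own size is about 5.4 to 6.5% at null rates of 25 to 75%. Simulation at null rates of 25 to 63%, with a baseline-adjusted hemoglobin test and correlation 0.9 to 0 in absolute value, gives 8.7 to 11.1% for either.

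**6. Two hemoglobin scales.** Section 6.4.2 puts both absolute and percent change into the primary analysis. If either may count, simulation under no effect (assumed baseline mean 8.5 g/dl with SD 1.0 to 1.5, SD of change 2 g/dl) gives 5.6 to 5.9%. The two scales are nearly the same test, so the excess is small.

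**7. What the mixed hypothesis leaves open.** A placebo mean of 1 does not fix the share transfused. If counts are Poisson, it is 1 − e⁻¹ = 63.2%, and Fisher power against 25% is 74%. If counts are negative binomial with dispersion k = 1, it is 1 − 1/2 = 50%, and power is 36%. Both distributions are assumed.

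**The case against.** The strongest reply is that the inferential text is consistent. Sections 6.4.1 and 6.4.2 speak of one primary endpoint, one alpha and a hemoglobin-only primary analysis, and 5.3.2 points the same way. The *and/or* in 4.2 sits in a research objective, which is not a decision rule. On that reading transfusion causes no inflation.

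Much of this stands. A reader might infer that the trial runs at a false-positive rate of nearly 10%. The documents do not support that, because no section says that either outcome suffices. A reader might also infer that transfusion has no analysis at all, which is too strong given the descriptive summary promised in 6.4.2. Nor is 7 to 10% a general figure: with Fisher's test and rare transfusion the error can be below 6%, and with linear regression on a yes/no outcome it can exceed 10%. The 5% comparator is itself slightly insecure because of the two hemoglobin scales.

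What does not stand is that the hemoglobin-only reading settles the matter. It requires setting aside the primary objective and the list of primary outcomes, each stated twice, and it leaves an outcome labelled primary without a named test.

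**Conclusion.** The contradiction is in the text and is certain: transfusion is primary in the synopsis, 4.2 and 5.2.1, is not primary in 6.4.1 and 6.4.2, is apparently secondary in 5.3.2, and is absent from the secondary lists. Its hypothesis cannot be tested as worded, and no success rule is given.

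The effect on error is conditional. It is nil if hemoglobin alone decides. If either outcome suffices, as 4.2 permits, the error is 7.0 to 9.75% for two tests of size 5%, roughly 6 to 8% with Fisher's test, and about 9 to 11% with linear regression on any transfusion. These figures rest on assumed two-sided tests, correlations and null transfusion rates. Counting both hemoglobin scales adds a smaller excess, to somewhat under 6% on its own under the assumed values.

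This should be fixed, but it does not make the trial uninterpretable. The early-stopping wording in 7.6 is a separate matter and is not part of this point.

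**What to change.** Before unblinding, replace *and/or* in the synopsis and 4.2, and make the synopsis, 4.1, 5.2.1, 5.3.2, 6.4.1 and 6.4.2 agree on one rule.

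Under either rule:
- Define the transfusion outcome as any PRBC transfusion from randomization to month 3 (yes/no). Restate its hypothesis as a rate in each arm.
- Name its test, for example Fisher's exact test, and exempt it from the linear-regression sentence in 6.4.2.
- Name one hemoglobin scale, absolute or percent change at 3 months with baseline adjustment, as primary. Make the other scale and the responder model supportive.

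The sponsor then chooses one of two equally acceptable rules:
- **(a)** Hemoglobin is the single primary at two-sided 0.05. Transfusion is the first key secondary, tested at 0.05 only if hemoglobin is significant.
- **(b)** Both stay primary, tested with Holm at overall two-sided 0.05.

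**Cost.** No extra patients or visits. Under (a), transfusion cannot be claimed if hemoglobin fails. Under (b), hemoglobin loses a few points of power. If each test has 80% power (assumed; correlation 0 to 0.9), transfusion is claimed 64 to 75% of the time under (a) and 75 to 78% under (b), and hemoglobin power under (b) is 75 to 78%. If transfusions raise placebo hemoglobin and cut its power to 50% (assumed), transfusion is claimed 40 to 50% of the time under (a) and 71 to 75% under (b). Restating the power in 6.4.1 on the chosen scale also needs an SD, which the sponsor must supply.

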### 4.3 Secondary Objectives (if applicable)

To determine the need for hospitalization for symptomatic anemia or acute gastrointestinal bleed

To determine the need for additional endoscopic interventions

To determine the rate of clinically significant side effects associated with TXA therapy leading to drug withdrawal

## 5 - Study Design

### 5.1 General Design Description

In the RCT portion of the study, we will enroll approximately 50 patients with diagnosed intestinal AEs through VCE and/or endoscopy who experience symptomatic anemia despite standard therapy including endoscopic ablation and iron supplementation. Subjects will be randomized to either the TXA treatment group versus the placebo treatment group for 3 months. Patients will have initial complete blood counts (CBC) measured as a baseline then subsequent CBCs measured at 1, 2 and 3 months. Patients will be monitored for drug side effects, symptoms related to anemia, the need for blood transfusions and hospitalizations related to GI bleeding/anemia.

#### 5.1.1 Study Date Range and Duration

The interventional portion of the study will be conducted over a 3-month period from March 2023 — May 2023. We will spend the months of December 2022 — February 2023 recruiting patients for the study and collecting demographic data on patients that meet inclusion and exclusion criteria. Following the interventional period of the study we will collect, interpret, analyze and summarize data from June — July 2023.

#### 5.1.2 Number of Study Sites

The study site includes the LSU Health Network GI Clinic at Ochsner Kenner Hospital

### 5.2 Outcome Variables

#### 5.2.1 Primary Outcome Variables

Primary outcome variables include hemoglobin concentration and the requirement of packed RBC transfusion.

#### 5.2.2 Secondary and Exploratory Outcome Variables (if applicable)

Secondary outcome variables include number of hospitalizations, endoscopic interventions (EGD, Colonoscopy, enteroscopy, video capsule endoscopy) and experienced side effects.

### 5.3 Study Population

All newly diagnosed Adult patients with intestinal angioectasias following at the LSU Health Network GI Clinic who meet screening criteria will be considered for inclusion. Existing patients with intestinal angioectasias that are currently not using TXA may also be approached for study participation.

#### 5.3.1 Number of Participants

The study design includes 50 participants enrolled in the study that meet inclusion/exclusion criteria.

#### 5.3.2 Eligibility Criteria/Vulnerable Populations

##### Inclusion Criteria

- Male, female, non-gender conforming patients aged >18 years with symptomatic anemia attributed to chronic GI blood loss from GI AEs despite endoscopic ablation and iron therapy
- Stated willingness to comply with all study procedures and availability for the duration of the study

**Exclusion Criteria**

- Contraindications to TXA therapy
  - Allergy to TXA, intracranial bleed, history of venous or arterial thromboembolism, active thromboembolic disease, ischemic retinopathy
- Bleeding/Coagulopathy disorder and/or on anticoagulation regimen
- Ulcerative colitis or Crohn's disease
- End stage renal disease
- Decompensated cirrhosis
- Pregnancy or intention to become pregnant
- Patient refusal of blood products because the secondary outcome is pre-determined
- Unable to give formal consent
- Participation in another interventional study where primary outcome includes hemoglobin/hematocrit values
- Inability to adhere to treatment regimen for 3 months
- Non-English speaking
- Patients < 18 years old

## 6 - Methods

### 6.1 Treatment - Drug

Tranexamic acid (TXA) is a hemostatic prescription medication available in the US and internationally. TXA is a synthetic reversible competitive inhibitor to the lysine receptor found on plasminogen. The binding of this receptor prevents plasmin from binding to and ultimately stabilizing the fibrin matrix. It is available in intravenous and oral formulations, however for this study we will focus on the oral regimen. Oral TXA has a half-life of up to 10 hours and a bioavailability of 50% resulting in the TID dosing regimen chosen for this study. TXA is currently FDA approved for menorrhagia and short-term prevention following tooth extraction in patients with hemophilia.

#### 6.1.1 Dosage, Admin, Schedule (if applicable)

Patients in the intervention group will be treated with TXA 650 mg three times per day for 3 months. This dosing regimen has been studied in patients with heavy menstrual bleeding and found to be beneficial with limited side effects.

#### 6.1.2 Method of Assignment/Randomization (if applicable)

Allocation concealment will be used to make sure the individual enrolling the trial subjects into the study has no bias towards group assignment. A statistician not directly involved in the analysis of the study will use simple randomization to create the two arms of the study (TXA vs placebo). Randomization will be carried out by using an online random number generating software, excluding the number zero. If an even number is generated, the patient will be placed in the TXA treatment arm, and if an odd number is generated the patient will be placed in the control (placebo) arm. This process will be repeated until there are 25 patients in each group.

#### 6.1.3 Packaging/Labelling

Both TXA and placebo will be packaged in identical bottles with similar labeling so participants and the research team will not be affected by bias.

#### 6.1.4 Storage Conditions

Both TXA and placebo will be stored at the Ochsner Kenner inpatient pharmacy prior to the start of the interventional portion of the study. Participants will pick up their medication from the pharmacy upon start of the trial.

## 6.2 Assessments

### 6.2.1 Safety/Pregnancy-related policy

Pregnancy is included in the exclusion criteria for this study. If female identifying participants were to consent to be part of the study, they will undergo a serum pregnancy testing prior to the start of the study

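### The only pregnancy test described is assigned by gender identity and has no stated date, so it does not fully match an exclusion that covers every participant

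*Combined protocol and SAP*

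**What the plan says.** Three parts of the combined protocol and SAP bear on who is admitted, excluded and tested.

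- **Admitted.** The inclusion criteria in section 5.3.2 open the trial to "Male, female, non-gender conforming patients aged >18 years with symptomatic anemia" attributed to angioectasias.
- **Excluded.** The exclusion criteria in the same section list "Pregnancy or intention to become pregnant", with no limit by sex or gender identity. Section 6.2.1 repeats this: "Pregnancy is included in the exclusion criteria for this study".
- **Tested.** Section 6.2.1 then gives the only test described: "If female identifying participants were to consent to be part of the study, they will undergo a serum pregnancy testing prior to the start". The start meant there is the study's, and no date is given for it.

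On timing, section 5.1.1 states "We will spend the months of December 2022 — February 2023 recruiting patients for the study" and places the interventional period in March to May 2023. Sections 6.3.3 and 6.3.4 put baseline laboratory work after enrollment and before the interventional portion, without a window. Section 6.1.4 has participants collect study medication from the pharmacy when the trial starts. Section 5.1 lists only blood counts at months 1, 2 and 3.

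**The concern.** The exclusion turns on a physical state, whereas the test is assigned by gender identity. The inclusion criterion itself treats male, female and non-gender-conforming patients as separate groups, so it is not a strained reading to say that the tested group is narrower than the group of admitted people who could be pregnant.

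The timing is open as well. A test that need only come before the study starts could be close to the first dose or well before it, depending on when the participant enrolls and when the sample is drawn.

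What is at stake is a safety exclusion. A participant with an unrecognised pregnancy could be randomized and given study drug although site staff had followed section 6.2.1 to the letter.

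**Working it through.** The point depends on no sample size, power or event count, and the plan gives no figure to reproduce. The check is a comparison of sections plus a count of calendar days.

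**Step 1: who is covered by each rule.**

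| Participant able to become pregnant | Admitted (5.3.2 inclusion) | Pregnancy excluded (5.3.2 exclusion) | Test assigned (6.2.1) |
|---|---|---|---|
| Identifies as female | Yes | Yes | Yes |
| Identifies as male | Yes | Yes | Not stated |
| Non-gender conforming, not identifying as female | Yes | Yes | Not stated |

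The exclusion applies in every row and the test in only one.

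**Step 2: what the untested rows amount to.** Section 6.3.4 has the inclusion and exclusion criteria reviewed at the screening and consent visit. A pregnancy that the participant knows of and reports, or an intended one, is caught there in every row without a test. What is left in the second and third rows is a pregnancy that is unrecognised or not disclosed.

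**Step 3: when the test can fall.** Section 6.2.1 makes the test conditional on consent, so it follows consent. No date is given beyond that. Assume that:

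- the test is drawn on the day of enrollment;
- enrollment runs over whole calendar months, from 1 December 2022 to 28 February 2023;
- dosing starts on 1 March 2023.

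The gap from test to first dose is then:

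- enrolled 1 December: 31 + 31 + 28 = 90 days;
- enrolled 28 February: 1 day.

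The range is about 1 to 90 days. A test drawn later than enrollment shortens the gap, and one taken just before dosing would also satisfy section 6.2.1.

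**Step 4: is there a later check?** Section 6.1.4 describes the pharmacy pick-up without a pregnancy re-check. That the test is done once is an inference from the single test described. The protocol does not say that it is done only once.

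**Step 5: how many patients.** Section 2.1, under pathophysiology and risk factors, says angioectasias are rarely seen below age 50 except in hereditary hemorrhagic telangiectasia. That condition is not named among the exclusions, and entry is open to adults of all ages, so the group is small but not empty. The documents give no age distribution from which to put a number on it.

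**The case against.** The strongest reply is that the exclusion does not depend on the test. It applies to everyone, it is reviewed before consent, and section 6.2.1 adds a test for one group without forbidding it for others. The reply continues that the remaining gap needs several uncommon things in one of about 50 patients: able to become pregnant, not identifying as female, and pregnant without knowing or saying so. All of this stands. It makes the point small, but the stated test still fails to reach part of the admitted population.

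Four stronger readings are tempting, and the documents do not support them.

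- **The test result will be about three months old at first dose.** Ninety days is the maximum of a range that rests on an assumed test at enrollment. The wording equally allows a test the day before dosing.
- **A patient who conceives after the test has slipped through screening.** That patient was correctly passed at screening. The accurate statement is narrower: no check is described between the test and drug pick-up that would detect the pregnancy before dosing.
- **A later pregnancy costs one patient in an arm of 25 (1/25 = 4%).** Section 7.3 continues follow-up and laboratory tests after study drug is stopped, and section 6.3.6 generally allows data collected before withdrawal to be kept. Stopping drug does not by itself remove a patient from the analysis.
- **The protocol has no provision at all for repeat testing.** The consent document is referred to as an attachment and is not part of the text reviewed, so the statement can be made only of the visible text.

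It is also fair to say that sections 5.3.2 and 6.2.1 do not flatly contradict each other. One is narrower than the other. Testing participants who identify as female but cannot become pregnant exposes nobody to harm.

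**Conclusion.** The point holds in a limited form. As written, section 6.2.1 leaves untested some admitted participants to whom the pregnancy exclusion applies, and the gap concerns unrecognised or undisclosed pregnancy only. The test has no stated date. Under an assumed draw at enrollment it precedes a 1 March start by about 1 to 90 days, and no re-check at pick-up is described in the visible text.

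Few patients are likely to be affected, and neither the sample size nor the analysis is touched. Severity is minor. It is worth correcting because it concerns a safety exclusion, staff should not have to guess whom to test or when, and the correction is cheap.

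**What to change.** In section 6.2.1, define the group to be tested by ability to become pregnant rather than by gender identity, so that the inclusion criteria, the exclusion criteria and the testing rule agree.

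The sponsor should also reconcile the timing of the test in section 6.2.1 with the recruitment and dosing dates in section 5.1.1 and the medication pick-up in section 6.1.4, and state when the test is due. The length of any window is for the sponsor to decide.

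The cost is a wording change and an occasional moved or repeated test. The design, sample size and analysis stay as they are.
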